1.4 CLINICAL HYPOTHESIS

This study aims to test the safety and tolerability of oral treprostinil in three cohorts of pediatric subjects aged 7 to 17 years: transitioning from IV/SC Remodulin, transitioning from inhaled prostacyclin, and as add-on to current PAH therapy in de novo prostacyclin subjects.

The hypothesis of this study is that stable PAH pediatric subjects can be safely be transitioned from IV/SC Remodulin to oral treprostinil therapy while maintaining the clinical benefit of the infused therapy. A recent study in stable, carefully-selected PAH adult subjects receiving IV/SC Remodulin demonstrated that subjects can be safely transitioned to oral treprostinil three times daily (TID) dosing under close medical observation without a significant decline in exercise capacity or worsening functional classification [White, 2014]. After analysis of interim pharmacokinetic data from this study, it was determined that a four times daily (QID) dosing regimen in select pediatric subjects may achieve a better pharmacokinetic profile than a TID regimen, potentially providing a clinical benefit. Additionally, we hypothesize that initiation of oral treprostinil in pediatric subjects following transition from inhaled prostacyclin or added to current PAH therapies in de novo prostacyclin subjects will result in clinical improvement compared to Baseline.

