6 DRUGS AND DOSING (OR TREATMENT PROCEDURES)

6.1 DRUG DOSAGE, ADMINISTRATION AND SCHEDULE

Oral treprostinil will be provided as 0.125 mg (blue), 0.25 mg (green), 1 mg (yellow) or 2.5 mg (pink) extended release tablets. Subjects/caregivers must be instructed to take the appropriate amount of 0.125 mg, 0.25 mg, 1 mg and/or 2.5 mg tablets based upon their prescribed dose.

Oral treprostinil will be dosed TID or QID at the discretion of the Investigator, with food. Dosing will take place approximately every 6 to 8 hours for TID dosing or approximately every 4 to 6 hours for QID dosing, with adjustments permitted based on the subject's lifestyle and schedule. Study subjects should take their study drug at approximately the same time each day.

Tablets must be swallowed whole and not chewed as this will result in inappropriate delivery of the active ingredient. If the tablet is inadvertently damaged during administration, the

Version: Amendment 2_FINAL_01Sep2016

subject/caregiver should contact site personnel in order to be monitored for the onset of symptoms due to possible inappropriate drug release.

For subjects receiving oral treprostinil TID, dosing frequency may be adjusted from TID to QID if clinically indicated, at the discretion of the Investigator. For applicable subjects, it is recommended, but not required, to take the total daily dose during TID dosing, and divide the total daily dose into a QID regimen using the closest, or lower, tablet strength as seen in the example table below. Dose modifications should always occur in accordance with Investigator judgment.

TID Dosing Regimen	Total Daily Dose with TID Dosing	QID Dosing Regimen	Total Daily Dose with QID Dosing
1.75 mg TID	5.25 mg	1.25 mg QID	5 mg
2.5 mg TID	7.5 mg	1.875 mg QID	7.5 mg
3.75 mg TID	11.25 mg	2.75 mg QID	11 mg
5.5 mg TID	16.5 mg	4.125 mg QID	16.5 mg
8.25 mg TID	24.75 mg	6.125 mg QID	24.5 mg
10 mg TID	30 mg	7.5 mg QID	30 mg

Example Transition from TID to QID Dosing of Oral Treprostinil

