6.1.1 Cohort 1: IV/SC Remodulin to Oral Treprostinil Transition

Once all entry criteria have been met and Baseline assessments completed, subjects should begin transition in the hospital from IV/SC Remodulin to oral treprostinil with a goal for complete transition off of IV/SC Remodulin within five days of the start of the transition. If possible, Day 5 (or final day of hospital stay if transition occurred in less than 4 days) of hospital stay should be reserved as an observational period for subjects successfully transitioned to oral treprostinil and no longer receiving IV/SC Remodulin. A cross titration will occur so that the dose of IV/SC Remodulin is decreased as the dose of oral treprostinil is increased. Once subjects have been transitioned off IV/SC Remodulin, the dose of oral treprostinil may continue to be titrated to the appropriate optimal dose for that subject throughout the rest of the study.

Dosing guidelines:

• The following equation can be used to estimate a comparable total daily dose of oral treprostinil (in mg) using the subject's dose of IV/SC Remodulin (in ng/kg/min) and weight (in kg):

Oral treprostinil total daily dose (mg) = 0.0072 x Remodulin dose (ng/kg/min) x weight

- IV/SC Remodulin should not be decreased more than 30 ng/kg/min within a 24 hour period
- Oral treprostinil should be increased in proportion to Remodulin decreases and the subject's weight
- IV/SC Remodulin doses should be adjusted (i.e., decreased) at the same time oral treprostinil dose is increased

Hospital Day	IV/SC Remodulin (ng/kg/min)	Oral Treprostinil (mg)		
Day 1 (0-24 hours)	Day 1 (0-24 hours)			
Morning (upon admission)	65	0		
Midday	59	0.5		
Evening	53	1		
Day 2 (24-48 hours)				
Morning	47	1.5		
Midday	41	2		
Evening	35	2.5		
Day 3 (48-72 hours)				
Morning	29	3		
Midday	23	3.5		
Evening	17	4.		
Day 4 (72-96 hours)				
Morning	11	4.5		
Midday	5	5		
Evening	0	5.5 (target dose)		
Day 5 (96-120 hours): Observational period prior to hospital discharge				
Morning	0	continue to titrate if appropriate		
Midday	0	continue to titrate if appropriate		
Evening	0	continue to titrate if appropriate		

Example TID Dosing Schedule for a 35 kg Subject:

Hospital Day	IV/SC Remodulin (ng/kg/min)	Oral Treprostinil (mg)	
Day 1 (0-24 hours)			
Morning (upon admission)	65	0	
Midday	61	0.25	
Early Evening (PM #1)	57	0.5	
Late Evening (PM #2)	53	0.75	
Day 2 (24-48 hours)			
Morning	48	1.125	
Midday	44	1.375	
Early Evening (PM#1)	40	1.625	
Late Evening (PM #2)	36	1.875	

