Day 3 (48-72 hours)			
Morning	30	2.25	
Midday	26	2.5	
Early Evening (PM #1)	22	2.75	
Late Evening (PM #2)	18	3	
Day 4 (72-96 hours)			
Morning	12	3.375	
Midday	8	3.625	
Early Evening (PM #1)	4	3.875	
Late Evening (PM #2)	0	4.125 (target dose)	
Day 5 (96-120 hours): Observational period prior to hospital discharge			
Morning	0	continue to titrate if appropriate	
Midday	0	continue to titrate if appropriate	
Early Evening (PM #1)	0	continue to titrate if appropriate	
Late Evening (PM #2)	0	continue to titrate if appropriate	

Example QID Dosing Schedule for a 35 kg Subject:

If necessary for subject safety, the transition from IV/SC Remodulin may extend beyond five days. Extended transitions must occur in hospital or subject must be willing and able to return to clinic as needed until the transition is complete. The transition must be completed by Week 4, or the subject will be withdrawn from the study. Once a subject has completely transitioned off IV/SC Remodulin, dose escalations of oral treprostinil should occur in either 0.125 mg or 0.25 mg increments every 24 hours, as tolerated. Sudden dose escalation or

TDE-PH-206

reductions should be avoided as they may lead to intolerable adverse effects or worsening of PAH. Gradual dose titrations are recommended to reduce the risk to subjects.

Routine contact between site personnel and the subject/caregiver should be conducted to monitor AEs and make decisions about dose titration between scheduled study visits. Dose changes may be made at any time up until five days prior to the Week 24 visit. Week 24 visit assessments can be performed over five days (120 hours) if needed; however, no oral treprostinil dose adjustments are allowed from five days prior to the Week 24 study visit, unless required to protect subject safety. All dose changes will be documented and captured in the eCRF.

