6.1.2 Cohort 2: Inhaled Prostacyclin to Oral Treprostinil Transition

Once all entry criteria have been met and Baseline assessments completed, dosing of oral treprostinil will be initiated at 0.125 mg TID or QID at the discretion of the Investigator, with food. Dosing will take place approximately every 6 to 8 hours for TID dosing or approximately every 4 to 6 hours for QID dosing, with adjustments permitted based on the subject's lifestyle and schedule. The first dose of 0.125 mg oral treprostinil should be taken at the study site. A cross titration will occur so that doses of inhaled prostacyclin will be decreased as oral treprostinil is increased. The transition must be completed by Week 4, or the subject will be withdrawn from the study.

Oral treprostinil dose escalations may occur every 24 hours (following three or four consecutive doses depending on TID or QID dosing, respectively) and should occur in increments of 0.125 mg TID or QID, at the discretion of the Investigator, during the first four weeks of the study as clinically indicated. Following four weeks of treatment, dose escalations may occur in either 0.125 mg or 0.25 mg increments every 24 hours, as tolerated. Sudden dose escalations or reductions should be avoided as they may lead to intolerable adverse effects or worsening of PAH. Gradual dose titrations are recommended to reduce the risk to subjects.

Routine contact between site personnel and the subject/caregiver should be conducted to monitor AEs and make decisions about dose titration between scheduled study visits. Dose

Version: Amendment 2_FINAL_01Sep2016

changes may be made at any time up until five days prior to the Week 24 visit. Week 24 visit assessments can be performed over five days (120 hours) if needed; however, no oral treprostinil dose adjustments are allowed from five days prior to the Week 24 study visit, unless required to protect subject safety. All dose changes will be documented and captured in the eCRF.

6.1.3 Cohort 3: Addition of Oral Treprostinil to Background PAH Therapy (De Novo Prostacyclin Subjects)

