## ABBREVIATIONS AND DEFINITIONS

Abbreviation	Definition
6MWD	6-Minute Walk Distance
6MWT	6-Minute Walk Test
AE	Adverse Event
ALT	Alanine Aminotransferase
AST	Aspartate Aminotransferase
BUN	Blood Urea Nitrogen
cMRI	Cardiac Magnetic Resonance Imaging
CPET	Cardiopulmonary Exercise Testing
CSR	Clinical Study Report
DSMB	Data Safety Monitoring Board
ECG	Electrocardiogram
eCRF	Electronic Case Report Form
ERA	Endothelin Receptor Antagonist
IQR	Interquartile Range
IV	Intravenous(ly)
LOCF	Last Observation Carried Forward
LV	Left Ventricular
LVEDP	Left Ventricular End-Diastolic Pressure
LVEF	Left Ventricular Ejection Fraction
MedDRA	Medical Dictionary for Regulatory Activities
NT-proBNP	N-Terminal Pro-Brain Natriuretic Peptide
PAH	Pulmonary Arterial Hypertension
PDE5-I	Phosphodiesterase Type 5 Inhibitor
PedsQL	Pediatric Quality of Life Inventory
PK	Pharmacokinetic(s)
PT	Preferred Term
QOL	Quality of Life
RV	Right Ventricular
RVEDV	Right Ventricular End-Diastolic Volume
RVEF	Right Ventricular Ejection Fraction
SAE	Serious Adverse Event
SAP	Statistical Analysis Plan
SC	Subcutaneous
SD	Standard Deviation
sGC	Soluble Guanylate Cyclase
SOC	System Organ Class
TEAE	Treatment-emergent Adverse Event

Abbreviation	Definition
TID	Three Times Daily
UTC	United Therapeutics Corporation
$VCO_2$	Carbon Dioxide Output
VE	Minute Ventilation
$VO_2$	Oxygen Uptake
WHO	World Health Organization
WHODD	World Health Organization Drug Dictionary

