## 11.1 EXTENT OF EXPOSURE

Oral treprostinil dosing will be listed by cohort and subject. The listing will include the date/time of initial oral treprostinil dose, the initial dose (mg), and all subsequent dose changes with start date, morning dose, midday dose, and evening dose.

Remodulin dosing will be listed by subject for Cohort 1 subjects only. The listing will include the initial Remodulin dose (ng/kg/min) and all changes during the study, including the start date/time of the new dose as well as the new dose (ng/kg/min).

Tyvaso dosing will be listed by subject for Cohort 2 subjects only. The listing will include the number of initial Tyvaso breaths per session, the number of initial Tyvaso sessions per day, and all changes during the study; including the start date of new dose, number of breaths per session, and number of sessions per day.

Ventavis dosing will be listed by subject for Cohort 2 subjects only. The listing will include the initial Ventavis dose (X mcg with X mcg/mL), the number of initial Ventavis sessions per

day, and all changes during the study, including the start date of new dose, new dose, and number of sessions per day.

The oral treprostinil dosing and exposure summary will include descriptive statistics for initial oral treprostinil dose, oral treprostinil dose when Remodulin dose is 0.0, oral treprostinil dose at time of hospital discharge, oral treprostinil dose when subject is first off Tyvaso/Ventavis, and final oral treprostinil dose (mg) by cohort. Oral treprostinil dose will be calculated as the sum of the doses administered on a given day divided by the number of doses administered that day. The Remodulin dosing and exposure summary will include descriptive statistics for initial Remodulin dose (ng/kg/min). The Tyvaso dosing and exposure summary will include descriptive statistics for initial Tyvaso breaths per session and a categorical summary of number of initial Tyvaso sessions per day. The Ventavis dosing and exposure summary will include descriptive statistics for initial Ventavis dose per session and a categorical summary of number of initial Ventavis sessions per day.

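### SAP 11.1 summarises oral treprostinil as mean mg per administration without dosing frequency or daily dose, so a cohort with both TID and QID subjects is reported on two scales

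*SAP*

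**What the plan says.** SAP 11.1 (Extent of Exposure) defines the summarised oral treprostinil dose as "calculated as the sum of the doses administered on a given day divided by the number of doses administered that day". On that scale it reports, by cohort, five values: the initial dose, the dose once Remodulin has reached zero, the dose at hospital discharge, the dose when inhaled therapy has first stopped, and the final dose. These go into Table 14.1.10. The same section plans individual and mean dose plots by cohort and gives no separate definition of dose for them. The oral dosing listing names three daily slots (morning, midday, evening) and has no frequency field.

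The protocol supplied is Amendment 2, dated 01 Sep 2016. Section 1.4 explains why QID came in: from interim pharmacokinetic data, "it was determined that a four times daily (QID) dosing regimen in select pediatric subjects may achieve a better pharmacokinetic profile". Section 6.1 allows either regimen and a change from TID to QID during the study. For that change, "it is recommended, but not required, to take the total daily dose during TID dosing" and to divide it over four administrations. Section 6.1.2 says that in Cohort 2 "dosing of oral treprostinil will be initiated at 0.125 mg TID or QID at the discretion of the Investigator", and Section 6.1.3 does the same for Cohort 3. Section 6.1.1 states the Remodulin-to-oral conversion as a total daily dose.

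The SAP is dated 15 Aug 2017, and its Preface says it covers the original protocol and later amendments. Section 3 nevertheless describes TID dosing only. The abbreviation list expands TID as "Three Times Daily" and has no entry for QID, which appears nowhere in the supplied SAP text.

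**The concern.** Dividing the day's total by the number of doses removes frequency from the reported figure, and nothing else in the exposure summary puts it back. Within one regimen this does no harm: mg per dose orders subjects correctly. With both regimens in one cohort, the same number stands for different daily amounts, and the same daily amount appears as different numbers.

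The protocol expresses equivalence between regimens, and between Remodulin and oral treprostinil, in mg/day. That quantity cannot be read from Table 14.1.10. If the plots use the same definition, a subject switched from TID to QID at an unchanged daily dose would appear to step down by a quarter.

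The SAP handles its other intermittently dosed PAH drugs more fully. Section 9.4.4 summarises background drugs by total daily dose, and Section 11.1 gives Tyvaso and Ventavis an amount per session and a number of sessions per day. Only the study drug has neither a daily dose nor a frequency.

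**Working it through.** **Inputs.** The dose rule is from SAP 11.1. The six example TID-to-QID switches are from the table in Protocol 6.1. The conversion equation and the two 35 kg example schedules are from Protocol 6.1.1.

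**Step 1: reproduce the protocol's figures.** With t mg per dose on TID and q mg per dose on QID, daily dose is 3t or 4q. All six rows of the protocol's table reproduce exactly (below). For the 35 kg example starting at 65 ng/kg/min, the equation gives 0.0072 x 65 x 35 = 16.38 mg/day. Divided by 3 this is 5.46 mg (stated target 5.5) and divided by 4 it is 4.095 mg (stated target 4.125). Both stated targets amount to 16.5 mg/day: 5.5 x 3 and 4.125 x 4.

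**Step 2: apply the SAP rule to the same rows.** The rule returns 3t/3 = t on TID and 4q/4 = q on QID. On a switch the metric changes by q/t - 1, while daily dose changes by 4q/(3t) - 1.

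| TID mg per dose | TID mg/day | QID mg per dose | QID mg/day | Change in SAP metric | Change in daily dose |
|---|---|---|---|---|---|
| 1.75 | 5.25 | 1.25 | 5 | -28.6% | -4.8% |
| 2.5 | 7.5 | 1.875 | 7.5 | -25.0% | 0% |
| 3.75 | 11.25 | 2.75 | 11 | -26.7% | -2.2% |
| 5.5 | 16.5 | 4.125 | 16.5 | -25.0% | 0% |
| 8.25 | 24.75 | 6.125 | 24.5 | -25.8% | -1.0% |
| 10 | 30 | 7.5 | 30 | -25.0% | 0% |

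At equal daily dose 4q = 3t, so q/t = 0.75 and the metric is 25% lower on QID at any dose level. In reverse, a reported 5.5 mg means 5.5 x 3 = 16.5 mg/day on TID or 5.5 x 4 = 22 mg/day on QID, and 22/16.5 - 1 = 33%.

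**Step 3: check that the daily sum is comparable across regimens.** On Day 4 of the 35 kg schedules, TID gives 4.5 + 5 + 5.5 = 15.0 mg and QID gives 3.375 + 3.625 + 3.875 + 4.125 = 15.0 mg. The administered daily totals agree. The SAP metric gives 15.0/3 = 5.0 mg and 15.0/4 = 3.75 mg, which is 25% apart.

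**Step 4: cohort level, under assumptions.** The documents give no QID share. If every subject in a cohort had the same daily dose and a fraction f were on QID, the cohort mean of the metric would be t(1 - 0.25f). At 16.5 mg/day, t = 5.5 mg:

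| Assumed QID share | Cohort mean (mg) | Change from all-TID |
|---|---|---|
| 0% | 5.50 | 0% |
| 10% | 5.36 | -2.5% |
| 25% | 5.16 | -6.3% |
| 50% | 4.81 | -12.5% |
| 75% | 4.47 | -18.8% |

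These shares are illustrative and are not estimates for this trial.

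**The case against.** The strongest reply is that mg per administration is a legitimate clinical scale which the protocol itself uses: the example target doses and the dosing-interruption threshold are per-dose amounts. That stands. The fault is in pooling regimens without a label, and mg per dose should stay in the table. The contrast with the inhaled drugs is also weaker than it first looks, because their amount and session count are separate summaries of initial dosing and do not give a daily amount per subject.

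Three stronger readings are tempting, and the documents do not support them.

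- A reader might infer that mg/day is lost altogether. It is missing from the table, but a TID subject's daily dose can be rebuilt from the three listed doses. SAP Section 8 also says that everything in the locked database will be listed, so a fourth dose, if captured, should appear somewhere. A listing does not repair a pooled table or plot.
- A reader might infer that the starting dose in Cohorts 2 and 3 is misreported, because 0.125 mg reads the same for both regimens although a full day would be 0.125 x 3 = 0.375 mg or 0.125 x 4 = 0.5 mg. As a per-dose value 0.125 mg is correct. The first day may also be partial, so the full-day comparison is notional.
- A reader might infer a material understatement of exposure in this trial. The protocol speaks only of select subjects on QID, and no share is given.

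It is also fair to say that these outputs are descriptive. That limits the consequence, but the whole study is descriptive, so the exposure table is one of its main products.

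**Conclusion.** The point holds as a flaw in a stated rule. Followed as written, SAP 11.1 reports equal daily doses 25% apart whenever a cohort contains both regimens, and Amendment 2 had already made that possible in every cohort. The 25% is arithmetic and needs no assumption beyond equal daily dose; the range of 25.0% to 28.6% comes from the protocol's own example switches.

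The reach is limited. The effect is nil in a cohort on a single regimen, and its size for any cohort mean is unknown. It touches Table 14.1.10, and the dose plots only on the inference that they use the one dose definition given. The primary endpoint does not use this dose variable, and no dose-response analysis is planned, so neither is affected. It should be corrected because the correction is cheap and the unlabelled figure can mislead.

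**What to change.** In SAP 11.1:

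- Add total daily dose administered (mg/day) to the exposure summary. It is the numerator that the SAP rule already computes.
- Add the number and percentage of subjects on TID and on QID at each summary time point.
- Keep mg per dose, shown by regimen.
- Report the initial dose as mg per dose with the regimen, because the first day may be partial.
- State that the dose plots use total daily dose, or mark the regimen on them.
- Add a fourth daily dose and the dosing frequency to Listing 16.2.5.1.1.

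Bring the TID-only wording of SAP Section 3 into line with Amendment 2 and add QID to the abbreviations. As a minor and separate alignment, the pharmacokinetic listing in SAP Section 12 names no early-evening dose, which Protocol 3.3.3.1 places inside the sampling period for a QID subject assessed on the midday dose.

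The cost is SAP wording, one derived variable, one regimen row and minor reprogramming of a table, the plots and a listing. The protocol says that all dose changes are captured in the eCRF. The eCRF is not among the documents, so the sponsor must confirm that it holds the fourth dose and the dosing frequency. No treatment or dosing rule changes.

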### 11.2 BACKGROUND MEDICATION CHANGES

Endothelian receptor agonist, PDE5-I, and sGC stimulator dosing changes will be listed by cohort and subject. The listings will include if there were changes in the specific background medication (yes/no), the name of generic drug, the total daily dose, and the start date. The summary of background medication changes will include the number of subjects reporting any changes to each background medication type by cohort.

### 11.3 ADVERSE EVENTS

The AEs are collected from the time the informed consent form is signed until study termination. There are a number of AEs that are considered expected events given the underlying disease of study, PAH. These expected events attributable to PAH were not

recorded as an AE unless the event was serious or unusual with respect to intensity, frequency, or duration, or there was a reasonable possibility that it may have been caused by the study drug.

Adverse events will be coded using MedDRA PTs and SOC. All AEs reported in the eCRF will be listed, including non-treatment-emergent and treatment-emergent events.

Non-treatment-emergent AEs are defined as those AEs starting prior to the date of first oral treprostinil dosing. Treatment-emergent adverse events (TEAEs) are defined as those AEs starting on or after the date of first oral treprostinil dosing. The listing will include cohort, subject number, verbatim term, PT, SOC, treatment-emergent status, start/stop date, seriousness, severity, frequency, relationship to oral treprostinil, action taken with oral treprostinil, relationship to background medication, action taken with background medication, and outcome.

The TEAEs will be summarized first in an overall summary, which includes the number of subjects with at least 1 TEAE, at least 1 oral treprostinil attributable TEAE, at least 1 serious TEAE, at least 1 TEAE leading to oral treprostinil discontinuation, at least one background therapy attributable TEAE, at least one TEAE leading to background therapy discontinuation, and any fatal TEAEs. The overall summaries will also include the number of events for each of these categories.

Non-treatment-emergent AEs will be summarized by cohort using PTs. The PTs will be sorted by decreasing overall frequency.

The TEAEs and serious TEAEs will be summarized by cohort using SOC/PT and PT, separately. The summaries will include the number and percentage of subjects reporting and the number of events reported for each SOC/PT and each PT, respectively, for each cohort, in order of decreasing overall frequency, both within SOC and PT.

The TEAEs will be summarized by severity within PT. The TEAEs and serious TEAEs considered attributable to oral treprostinil will be summarized by SOC/PT and PT, as

described above. The TEAEs leading to oral treprostinil discontinuation will be summarized by PT.

